5.8 Criteria for Taking a Participant Off Protocol Therapy

Duration of therapy will depend on individual response, evidence of disease progression and tolerance. Treatment must discontinue regorafenib if any of the following criteria are met:

Disease progression by clinical evaluation or as documented by RECIST v 1.1.

- Intercurrent illness that prevents further administration of treatment
- Unacceptable adverse event(s)
- Drug is held for 28 days or longer
- Participant demonstrates an inability or unwillingness to comply with the oral medication regimen and/or documentation requirements
- Participant decides to withdraw from the protocol therapy
- General or specific changes in the participant's condition render the participant unacceptable for further treatment in the judgment of the treating investigator

Participants will be removed from the protocol therapy when any of these criteria apply. The reason for removal from protocol therapy, and the date the participant was removed, must be documented in the case report form (CRF). Alternative care options will be discussed with the participant.

A QACT Treatment Ended will be filled out when a participant is removed from protocol therapy. This form can be found on the QACT website or obtained from the QACT registration staff.

In the event of unusual or life-threatening complications, treating investigators must immediately notify the Overall PI, [name]

5.9 **Duration of Follow Up**

Participants will be followed through scans and visits until first progression or start of new cancer treatment regimen. Participants will be followed for survival for two years from study entry or until death-whichever occurs first.

5.10 Criteria for Taking a Participant Off Study

Participants will be removed from study when any of the following criteria apply:

- Lost to follow-up
- Withdrawal of consent for data submission
- Disease Progression by clinical evaluation or as documented by RECIST v1.1
- Death

The reason for taking a participant off study, and the date the participant was removed, must be documented in the case report form (CRF).

A QACT Off Study Form will be filled out when a participant comes off study. This form can be found on the QACT website or obtained from the QACT registration staff.

For Centralized Subject Registrations, the research team submits a completed Off Treatment/Off Study form to ODQ when a participant comes off study. This form can be found on the ODQ website or obtained from the ODQ registration staff.

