10. STUDY CALENDAR

Screening evaluations are to be conducted within 3 weeks prior to study registration. Scans and x-rays must be done \leq 4 weeks prior to study registration. In the event that the participant's condition is deteriorating, laboratory evaluations should be repeated within 48 hours prior to initiation of the next cycle of therapy.

Procedures	Screening	Treatment Cycle 1 Day 1 of			Treatment Cycle 2 Day 1 of		Treatment Cycle 3 and beyond Day 1 of	End Of Treatment	Follow up until first progression	After first progression. Follow up by phone until death ⁱ
			Week 2	Week 3	Week 1	Week 3	Week 1			
Clinic Visit	X	X	X	X	X	X	X			
Informed consent	X									
Demographics	X									
Medical history	X									
Concurrent meds	X	X	X	X	X	X	X	X		
Physical exam	X	X	X	X	X	X	X	X		
Vital signs	X	X	X	X	X	X	X	X		
Height	X									
Weight	X	X	X	X	X	X	X	X		
Performance status	X	X	X	X	X	X	X	X		
CBC w/diff, plts	X	X	X	X	X	X	X	X		
Serum chemistry ^a	X	X	X	X	X	X	X	X		
B-HCG ^b	X	X			X		X	X		
Urinalysis ^k	X	X	X	X	X	X	X	X		
UPCR ⁿ	X									
EKG	X	X						X		
CT/MRI/PET ^d	X	Xc						Xe	Xf	
Archival or fresh tumor biopsy	X			χm				Xm		
Tumor measurements	X						Xc	Xe	Xf	

Tumor markers ^g	X	X			X		X	X		
QOL questionnaire ^h		χl		X	X	X	X	X	X	
Regorafinib		Once d	Once daily, weeks 1-3 in each cycle							
Adverse Events ^j			X							

- a) Albumin, alkaline phosphatase, total bilirubin, bicarbonate, BUN, calcium, chloride, creatinine, glucose, LDH, phosphorus, potassium, total protein, SGOT [AST], SGPT [ALT], sodium, INR, PT and PTT.
- b) Serum pregnancy test (women of childbearing potential). b-HGG testing for women of childbearing potential should be done prior to the initiation of each cycle.
- c) Every 8 weeks until first progression, death, or 24 months from study registration whichever occurs first (also obtain a survival status update at each visit).
- d) The same imaging modality should be used throughout the study.
- e) In subjects who discontinue study therapy without confirmed disease progression, a tumor assessment should be performed at end of treatment (i.e. date of discontinuation +/- 4 week window). If a previous scan was obtained within 4 weeks prior to end of treatment date then a scan at end of treatment is not mandatory.

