- f) Post end of protocol treatment, if first progression has not yet been confirmed, tumor assessments are to continue every 2 months (+/- 7 days) until first progression, start of new cancer treatment regimen, death, or 24 months from study registration, whichever occurs first.
- g) Serum calcitonin, carcinoembryonic antigen (CEA), CA 19-9 for MTC, Thyroglobulin, TSH and free T4 in DTC.
- h) MD Anderson Symptom Inventory Thyroid (MDASI-Thy)
- i) After first progression, participants will be followed by phone only, every 3 months (+/- 2 weeks) for 24 months from study registration or until death whichever occurs first.
- j) Patients will be assessed monthly for adverse events; until first disease progression.
- k) Full urinalysis (dipstick plus microscopic evaluation) at the Screening and End-of-Treatment visits and a basic urinalysis (dipstick only) at each visit indicated prior to administration of trial drug. If the basic urinalysis is abnormal, then a full urinalysis should be performed.
- 1) Patient needs to complete this timepoint prior to starting protocol therapy.
- m) For patients with accessible tumors. Optional but strongly encouraged.
- n) Patients with persistent proteinuria \geq Grade 3 NCI-CTCAE v4.0 are excluded.

Assessments must be performed prior to study registration. Study assessments and agent should be administered within ± 3 days of the protocol-specified date, unless otherwise noted. Biological Sample Collection:

Sample Type	Screening	1 2	End of Treatment
		Week 3	
Blood (whole blood with EDTA)	X	X	X
Archived tumor	X		
Fresh Biopsy	Xa	Xb	Xb

- a) Fresh screening biopsy required for patients without sufficient archival tumor tissue.
- b) For patients with accessible tumors. Optional but strongly encouraged.
- c) For participating sites that are not Dana-Farber Cancer Institute, fresh biopsy and blood will be stored at -80°C until they can be sent to Dana-Farber Cancer Institute.

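### Section 5.10 takes patients off study at progression, the event after which Section 5.9 and the study calendar require survival follow-up to continue

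*Combined protocol and SAP*

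**What the plan says.** Section 5.10 removes a participant from study when any one of four criteria applies: loss to follow-up, withdrawal of consent for data submission, death, and "Disease Progression by clinical evaluation or as documented by RECIST v1.1".

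Three other places assume that follow-up goes on after progression:

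- **Section 5.9** ends scans and visits at first progression or new cancer treatment, but then states: "Participants will be followed for survival for two years from study entry", or until death if earlier.
- **Study calendar (Section 10), last column**, is headed "After first progression. Follow up by phone until death".
- **Study calendar, footnote i:** "After first progression, participants will be followed by phone only, every 3 months", up to 24 months from registration or death.

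Section 5.8, the separate list for stopping protocol therapy, already contains "Disease progression by clinical evaluation or as documented by RECIST v 1.1".

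Section 11.1.6 defines OS from registration to death, with censoring at the date last known alive. Section 13.1 uses Kaplan-Meier for time-to-event endpoints.

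**The concern.** Read literally, 5.10 ends participation at the event that opens the telephone schedule. No sentence says that a patient taken off study at progression stays in survival follow-up.

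OS depends on those calls. Calendar footnote c says to "also obtain a survival status update at each visit", but only until first progression. After that, the calls are the only scheduled source of vital status. If they are not made, a patient's last known alive date falls at about progression, and patients leave the risk set just as their risk of death is likely to rise. That is informative censoring, and it overstates OS. Contacts missed at the time may not be recoverable later.

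A narrower conflict concerns patients with clinical progression that scans have not confirmed. Footnote f continues tumor assessments every 2 months while first progression is unconfirmed, and the note on symptomatic deterioration in Section 11.1.4.4 asks for objective progression to be documented after treatment ends. Section 5.10 would take these patients off study first. For progression documented by RECIST, footnote f also stops the scans, so there is no conflict with it.

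**Working it through.** **Can off study mean off therapy?** The text points against it.

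- Section 5.8 already makes progression an off-therapy criterion, so on that reading the 5.10 entry would be redundant.
- The other three 5.10 criteria all end data collection.
- The forms differ. Section 5.8: "A QACT Treatment Ended will be filled out when a participant is removed from protocol therapy". Section 5.10: "A QACT Off Study Form will be filled out when a participant comes off study".

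**Do the follow-up lengths agree?** Two years from study entry (5.9) and 24 months from registration (footnote i) match if entry means registration. The calendar column header gives no cap; footnote i supplies it. The conflict is therefore about progression only.

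**How many patients are exposed?** The plan gives no figure to reproduce. Inputs:

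- 20 evaluable DTC patients (Section 13.1).
- Exponential progression-free survival (PFS) with median 10.8 or 18.3 months: the sorafenib and lenvatinib results in Section 2.2, so other drugs.
- Assumed share *f* of PFS events that are deaths: 5% to 20%.

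With λ = ln 2 / median, PFS(24) = exp(−24λ):

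- Median 10.8: PFS(24) = 0.214. Events = 20 × (1 − 0.214) = 15.7. Progressions = 15.7 × 0.80 to 15.7 × 0.95 = 12.6 to 14.9.
- Median 18.3: PFS(24) = 0.403. Events = 20 × (1 − 0.403) = 11.9. Progressions = 9.5 to 11.3.

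So about 10 to 15 of 20 patients would progress by 24 months.

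**How many calls are lost?** Progression at 10.8 months puts calls at 13.8, 16.8, 19.8 and 22.8 months: 4 lost. Progression at 18.3 months puts calls at 21.3 and, within the 2-week window, 24.3 months: 1 or 2 lost.

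**What does this do to 24-month OS?** Further assumptions: median post-progression survival *m* of 12, 18 or 24 months (μ = ln 2 / m); a share *r* of progressing patients removed at progression with no later vital status; *f* = 0.05, 0.10 or 0.20.

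- Alive without progression: S(t) = exp(−λt)
- Alive after progression: P(t) = (1 − f) · λ/(λ − μ) · [exp(−μt) − exp(−λt)]
- True OS(24) = S(24) + P(24)
- Kaplan-Meier OS(24) = exp{−∫₀²⁴ [fλS + μ(1 − r)P] / [S + (1 − r)P] dt}, integrated numerically

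The direction is upward because the death hazard after progression exceeds that before it throughout the grid: the smallest μ is ln 2/24 = 0.029 per month, and the largest fλ is 0.20 × 0.064 = 0.013.

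| Removed (r) | Gap, PFS median 10.8 (points) | Gap, PFS median 18.3 (points) |
|---|---|---|
| 10% | 0.5 to 1.6 | 0.7 to 1.7 |
| 25% | 1.4 to 4.5 | 1.8 to 4.5 |
| 50% | 3.3 to 10.7 | 4.0 to 10.2 |

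In every row the smallest gap is at f = 0.20, m = 24 and the largest at f = 0.05, m = 12. For example, with median 10.8 and r = 50%, true 0.630 is estimated as 0.663 at the small end, and true 0.553 as 0.661 at the large end. In the limit where every site applies 5.10 (r = 100%), the grid gives about 10 to 37 points.

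**The case against.** The strongest reply is that the intent is plain. Section 5.9, the calendar column and footnote i agree and are specific; against them stands one generic bullet, perhaps copied from 5.8, which would leave a whole calendar column empty. Nothing shows that any site would follow it. This is fair, and it is why the bias is conditional. It does not remove an explicit instruction in 5.10 with its own form.

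Other points:

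- **Forms.** Section 5.10 also mentions a combined Off Treatment/Off Study form for centralized registrations. This weakens the argument from separate forms. The duplicated criterion in 5.8 and the nature of the other 5.10 criteria still carry the reading.
- **Other sources of deaths.** Section 7.6.3.13 requires reporting of deaths during the trial or within 30 days of the end-of-treatment visit, and a last known alive date need not come from a scheduled call. Some early deaths would be captured, so giving removed patients no later vital status is somewhat severe. This does not replace contact to month 24.
- **Importance.** OS is not among the objectives in 1.2 and 1.3, and Section 13.1 does not name it. Response and the 10-month progression-free proportion do not use survival after progression. This stands and limits the severity.
- **Precision.** With 20 patients, the binomial standard error √[p(1 − p)/20] is about 11 points at p = 0.55 and 10 at p = 0.73. The largest gap at 50% removal is about one standard error. That is a fair scale, but bias adds to sampling error, and this bias is avoidable.
- **Exposure count.** The 8 patients enrolled with medullary thyroid cancer are not in it.
- **Footnote f.** It does not define confirmed progression as RECIST-only, so the narrower conflict depends on reading the word that way. Section 11.1, which evaluates progression by RECIST 1.1, supports that reading.

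**Conclusion.** The concern holds. The off-study rule in 5.10 contradicts the survival follow-up required by 5.9, the calendar's telephone column and footnote i. The rule is wrong as written, rather than short of detail.

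The bias in OS is upward to the extent that sites apply 5.10. The size cannot be derived from the documents, because neither the share of patients removed nor post-progression survival is given. The tabulated gaps are illustrations resting on exponential times, PFS medians from other drugs, and assumed values for the removal share, post-progression survival and the death share of PFS events. The contradiction itself rests on none of these.

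The correction should be made, but it does not threaten the trial's primary conclusions: the DTC two-stage response decision is untouched.

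**What to change.** Reconcile 5.10 with 5.9 and calendar footnotes f and i. Take progression off the off-study list, keep loss to follow-up, withdrawal of consent and death, and add completion of 24 months from registration. The survival calls, and the footnote f assessments for patients without confirmed progression, then proceed as already scheduled.

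The cost is a wording change in 5.10 alone. No visit, scan or call is added. No change to the treatment-stopping criteria in 5.8 is proposed.

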6. DOSING DELAYS/DOSE MODIFICATIONS

Dose delays and modifications will be made as indicated in the following table. The descriptions and grading scales found in the revised NCI Common Terminology Criteria for Adverse Events (CTCAE) version 4.0 will be utilized for dose delays and dose modifications. A copy of the CTCAE version 4.0 can be downloaded from the CTEP website http://ctep.cancer.gov/ProtocolDevelopment/electronic_applications/ctc.htm.

The starting dose of regorafenib is 80 mg once daily. Regorafenib will be administered on a 3 weeks on/1 week off schedule [3 weeks out of every 4]. The dose will be escalated in the first cycle to 160 mg at the investigator's discretion if toxicities observed are <grade2. The maximum tolerated dose in cycle 1 will be given in cycle 2 and onwards.

Doses will be delayed or reduced for clinically significant hematologic and non-hematologic toxicities that are related to protocol therapy according to the guidelines shown in the Dose Delays/Dose Modifications table that follows. Dose modifications will follow predefined dose levels. Dose adjustments for hematologic toxicity are based on the blood counts obtained in preparation for the day of treatment.

The modifications of regorafenib will follow the following predefined dose levels:				
160 mg daily Four 40-mg tablets of regorafenib				
120 mg daily Three 40-mg tablets of regorafenib				
80 mg daily Two 40-mg tablets of regorafenib				
40 mg daily One 40-mg tablet of regorafenib				

If a subject experiences more than one toxicity, dose reduction should be according to the toxicity with the highest grade. In the case of two or more toxicities of the same grade, the investigator may dose reduce according to that deemed most causally related to study treatment.

The following tables outline dose adjustments for toxicities related to study drug except hand-foot skin reaction, hypertension and liver function test abnormalities.

Table 1: Recommended dose modification for toxicities except hand-foot-skin reaction, hypertension and ALT/ST/bilirubin			
NCI-CTCAE v4.0 ^a	Dose Interruption	Dose Modification ^b	Dose for Subsequent Cycles
Grade 0-2	Treat on time	No change	No change

Grade 3	Delay until :S Grade 2 ^c	Reduce by 1 dose level	If toxicity remains <	
			Grade 2, dose re-	
			escalation can be	
			considered at the	
			discretion of the	
			treating investigator. If	
			dose is re-escalated	
			and toxicity (2: Grade	
			3) recurs, institute	
			permanent dose	
			reduction.	
Grade 4	Delay until :S Grade 2°	Reduce by 1 dose		
		level.		
		Permanent		
		discontinuation		
		can be considered at		
		treating investigator's		
		discretion.		
a NCI CTCAE - National Conson Institute. Common Tomain along Critario for Advance Events				

a. NCI-CTCAE = National Cancer Institute - Common Terminology Criteria for Adverse Events, version 4.0

The table above outlines dose adjustments for hematologic and non-hematologic toxicities related to regorafenib except HFSR, hypertension and ALT/ST/bilirubin.

In addition to these recommended dose modifications, subjects who develop diarrhea, mucositis, anorexia or other events predisposing to fluid loss or inadequate fluid intake should be carefully monitored and rehydrated as clinically necessary. This is in order to minimize the risk of postural hypotension and renal failure.

Table 2: Grading for Hand-Foot-Skin-Reaction				
	Grade 1	Grade 2	Grade 3	
NCI-CTCAE v4.0 Palmar-plantar erythrodysesthesia syndrome ^a	Minimal skin changes or dermatitis (e.g., erythema, edema, or hyperkeratosis) without pain	(e.g., peeling, blisters	Severe skin changes (e.g., peeling, blisters, bleeding, edema, or hyperkeratosis) with pain	
	Numbness, dysesthesia / paresthesia tingling, painless swelling, or erythema of the hands and/or feet	swelling of the hands	Moist desquamation, ulceration, blistering, or severe pain of the hands and/or feet	

b. Excludes alopecia, non-refractory nausea/vomiting, non-refractory hypersensitivity and nonclinical and asymptomatic laboratory abnormalities.

c. If no recovery after a 4 week delay, treatment should be permanently discontinued unless subject is deriving clinical benefit.

Effect on activities	Does not disrupt normal activities	activities of daily life (e.g., preparing	undressing, feeding self, using the toilet, taking	
a. Palmer-planter erythrodysesthesia syndrome is a disorder characterized by redness, marked discomfort, swelling, and tingling in the palms of hands or the soles of the feet.				

Grade of event (NCI-CTCAE v4.0)	Occurrence	Suggested Dose Modification
Grade 1	Any	Maintain dose level and immediately institute supportive measures for symptomatic relief
Grade 2	1 st occurrence	Consider decreasing dose by one dose level and immediately institute supportive measures. If no improvement, interrupt therapy for a minimum of 7 days until toxicity resolves to Grade 0-1 b, c
		Interrupt therapy until toxicity resolves to Grade 0-1.° When resuming treatment, treat at reduced dose level b
	3 rd occurrence	Interrupt therapy until toxicity resolves to Grade 0-1. When resuming treatment, decrease dose by one dose level. b, d
	4 th occurrence	Discontinue therapy
Grade 3	1 st occurrence	Institute supportive measures immediately. Interruptherapy for a minimum of 7 days until toxicity resolves to Grade 0-1. ^c When resuming treatment, decrease dose by one dose level. ^{b, d}
	2 nd occurrence	Institute supportive measures immediately. Interrupt therapy for a minimum of 7 days until toxicity resolves to Grade 0-1. ^c When resuming treatment, decrease dose by one additional dose level ^{b, d}
	3 rd occurrence	Discontinue treatment permanently.

a. More conservative management is allowed if judged medically appropriate by the investigator.

At first occurrence of HFSR, independent of grade, prompt institution of supportive measures such as topical emollients, low potency steroids, or urea-containing creams should be administered.

b. If toxicity returns to Grade 0-1 after dose reduction, dose re-escalation is permitted at the discretion of the investigator if subject has completed one cycle at reduced dose without recurrence of event.

c. If there is no recovery after a 4-week delay, treatment with regorafenib will be discontinued permanently.

d. Subjects requiring > 2 dose reductions should go off protocol therapy.

6.1 Recommended prevention/management strategies for skin toxicities consistent with HFSR are summarized below:

6.1.1 **Control of calluses**

Before initiating treatment with regorafenib:

- Check condition of hands and feet.
- Suggest a manicure/pedicure, when indicated.
- Recommend pumice stone use for callus or 'rough spot' removal.

During regorafenib treatment:

- Avoid pressure points.
- Avoid items that rub, pinch or create friction.

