1. OBJECTIVES

1.1 Study Design

This is an open label, non-randomized, phase II study designed to evaluate the efficacy and safety of regorafenib in subjects with progressive, metastatic medullary thyroid carcinoma (MTC) and in subjects with differentiated thyroid cancer (DTC) with or without prior therapy. A total of up to 32 patients could be enrolled in this study (8 with medullary thyroid cancer, and up to 24 with RAI refractory thyroid cancer) which is similar to the overall accrual goal from when the trial originally opened. Given the changing treatments for medullary thyroid cancer, enrollment to the medullary thyroid cancer cohort is held and up to 24 patients with RAI refractory thyroid cancer will be enrolled. Eligible subjects with RAI refractory thyroid cancer will be enrolled on a dose escalation schedule that has been established recently (starting at 80mg and escalation weekly to 120 and 160mg if no severe SAE occur and continuing on the individual MTD from cycle 2 onward) with regorafenib daily on a three weeks on and one week off schedule.

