6.2 Hypertension

Hypertension is a known AE associated with regorafenib treatment. Subject will have their blood pressure measured at visits 1,2,3,4, and 5 during the first 6 weeks of treatment. If additional blood pressure measurements are done outside the study site, and the blood pressure is > 140 mm Hg systolic or > 90 mm Hg diastolic (NCI CTCAE v4.0), then the subject must contact study personnel. The management of hypertension, including the choice of antihypertensive medication, will be performed according to local standards and to the usual practice of the investigator. Every effort should be made to control blood pressure by medical means other than study drug dose modification. If necessary, Table 6-4 outlines suggested dose reductions.

Table 4: Management of Treatment-Emergent Hypertension				
Grade (CTCAE v4.0)	Antihypertensive Therapy	Regorafenib Dosing		

Prehypertension (systolic BP 120 - 139 mmHg or diastolic BP 80 - 89 mmHg)	None	 Continue regorafenib Consider increasing blood pressure (BP) monitoring 	
Symptomatic increase by > 20 mmHg (diastolic) if previously within normal	 If BP previously within normal limits, start anti- hypertensive monotherapy 	 Continue regorafenib If symptomatic, hold regorafenib until symptoms resolve AND diastolic BP:S 90 mm Hg^a. When regorafenib is restarted, continue at the same dose level. 	
diastolic BP 2: 100 mmHg OR More than one drug or more		 When regorafenib is restarted, continue at the same dose level. If BP is not controlled with the addition of new or more intensive therapy, reduce by 1 dose level.^b 	
Life-threatening consequences (eg, malignant hypertension, transient or permanent neurologic deficit, hypertensive crisis)	Per institutional guidelines	Discontinue therapy	
 a. Patients requiring a delay of >4 weeks should go off protocol therapy b. If BP remains controlled for at least one cycle, dose re-escalation permitted per investigator's discretion. c. Patients requiring >2 dose reductions should go off protocol therapy. 			

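### Section 5.8 requires stopping at a 28-day hold with no exception, while Table 1 footnote c excepts a benefiting patient whose toxicity has not recovered after 4 weeks

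*Combined protocol and SAP*

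**What the plan says.** **Off-therapy rule, Section 5.8.** The list opens with "Treatment must discontinue regorafenib if any of the following criteria are met", includes "Drug is held for 28 days or longer", and is followed by "Participants will be removed from the protocol therapy when any of these criteria apply". The hold criterion has no exception. The reason for removal and its date must be entered in the case report form.

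**General toxicity rule, Section 6, Table 1.** The table covers drug-related toxicities except hand-foot skin reaction, hypertension and ALT/AST/bilirubin. Its grade 3 and grade 4 rows delay dosing, and footnote c is attached to that delay: "If no recovery after a 4 week delay, treatment should be permanently discontinued unless subject is deriving clinical benefit".

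**Toxicity-specific rules.** The hand-foot skin reaction dosing table, footnote c: "If there is no recovery after a 4-week delay, treatment with regorafenib will be discontinued permanently". Section 6.2, Table 4 (hypertension), footnote a: "Patients requiring a delay of >4 weeks should go off protocol therapy". Neither contains a benefit exception.

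**Cycle 1 escalation (editorial note only).** Section 1.1 has "escalation weekly to 120 and 160mg if no severe SAE occur". Section 6 leaves escalation to the investigator's "discretion if toxicities observed are <grade2". Section 5.1 uses SDRT without a grade and then SCRT. Section 8.1.3 refers to toxicity and investigator discretion without a threshold.

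**The concern.** Two current sections state a stopping rule for the same event at the same time point, and they differ for one group of patients. The group is those with an unresolved Table 1 toxicity, grade 3 or 4 when dosing was interrupted, who are judged to be benefiting. If such a patient stays on protocol therapy past 28 days, a site or monitor could call it compliant under Table 1 or a deviation under Section 5.8.

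The discontinuation date also matters for the data. It is recorded with its reason, and under Study Calendar footnote e it anchors the end-of-treatment scan for patients who stop without confirmed progression. Different readings at different sites would give different off-treatment dates for similar patients.

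**Working it through.** The plan gives no figure for this point, so the check is mainly a comparison of text.

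**1. Does footnote c belong to Table 1?** In the available text it is printed below the hand-foot skin reaction grading table. However, Table 1 carries the b and c markers (on the dose-modification heading and on the grade 3 and 4 delays), and the hand-foot skin reaction dosing table has its own footnotes a to d. Footnote c is therefore Table 1's.

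**2. Is a delay the same thing as a hold?** Table 1 lists the delay under dose interruption, so the patient is off drug.

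**3. Do the limits coincide?** 4 weeks × 7 days = 28 days.

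**4. Outcome for a patient unrecovered at that point:**

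| Toxicity | Section 5.8 | Toxicity table |
|---|---|---|
| Table 1, no clinical benefit | stop | stop |
| Table 1, clinical benefit | stop | excepted |
| Hand-foot skin reaction | stop | stop |
| Hypertension | stop from day 28 | stop from day 29 (more than 4 weeks) |

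Only the second row is a substantive conflict. The fourth differs by one day on a common count.

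**5. When does the conflict begin?** The documents do not say whether the planned 7-day break counts towards the hold.

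- Break counts: 28 days after the last dose.
- Break does not count, and one break falls inside the hold: 28 + 7 = 35 days.
- Break does not count, the 28-day cycle calendar keeps running, and the last dose was on days 15 to 21: two breaks fall inside the hold, so 28 + 14 = 42 days. Example with the last dose on day 21: break on days 22–28, 21 missed doses on days 29–49, break on days 50–56, 7 missed doses on days 57–63; 63 − 21 = 42.

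The starting day moves with the convention. The contradiction is present under each.

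**6. Is the design affected?** The DTC design enrols 9 evaluable patients, stops at 2 or fewer responses, and otherwise continues to 20, where 8 or more are needed.

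- Early stop at a 25% response rate: P(X ≤ 2 | 9, 0.25) = 0.0751 + 0.2253 + 0.3003 = 0.601 (stated 60%).
- Declared effective: the sum over x = 3 to 9 of P(X₁ = x | 9) × P(X₂ ≥ 8 − x | 11). This is 0.090 at 25% (stated 9%) and 0.806 at 49% (stated 81%).

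The hold rule is not an input to any of these. The primary efficacy population in Section 13.1 is all eligible patients who begin treatment. Under Study Calendar footnote f, tumour assessments continue after treatment ends until first progression, new treatment, death or 24 months.

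**The case against.** The strongest defence is that Section 5.8 already settles the matter. It uses must, whereas Table 1 is headed as recommended and footnote c uses should. A careful site would stop at 28 days and comply with both passages. The difference in force is real, and so is the point that stopping is always compliant. But Section 6 opens by saying that delays and modifications will be made as its table indicates, and a reader who lets the specific rule govern the general one would reach the opposite answer. No precedence clause decides between them.

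Four stronger readings are tempting and are not supported:

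- **Every unrecovered toxicity is affected.** It is not. Hand-foot skin reaction and hypertension, both prominent among the severe events cited in Section 2.3.2, have no benefit exception.
- **Continuation is unlimited.** Footnote c sets no time limit of its own, but the other Section 5.8 criteria still apply, including progression, unacceptable adverse events and investigator judgment.
- **Footnote c authorises dosing through an unrecovered toxicity.** It does not say that dosing resumes. The conflict does not need this: a patient merely kept on hold past 28 days must be removed under Section 5.8 and is excepted from permanent discontinuation under footnote c.
- **The escalation wordings are a second contradiction of equal weight.** The sharpest version has a non-serious grade 2 toxicity passing Section 1.1 and failing Section 6. It depends on a strict less-than sign, and comparison signs are visibly damaged elsewhere in the available text. Sections 6 and 8.1.3 also leave escalation to discretion. What remains is an ungraded SDRT, an apparent typing slip in SCRT, and inconsistent wording.

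**Conclusion.** The contradiction between Section 5.8 and Table 1 footnote c is established with high confidence, because it lies in words rather than in comparison signs. It covers one group: patients with a Table 1 toxicity unrecovered at the 4-week limit who are deriving clinical benefit. For them only continuation is in doubt. It rests on assigning footnote c to Table 1 and on treating a dose delay as a hold, both of which the table's own markers and column headings support.

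How many patients would be affected cannot be calculated from the documents. The operating characteristics do not change. The point should be fixed because it concerns continued therapy with an unresolved grade 3 or 4 toxicity. The one-day hypertension difference and the escalation wording are tidying items.

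**What to change.** The sponsor should reconcile Section 5.8 with Table 1 footnote c, and align Table 4 footnote a, so that one hold rule is stated identically wherever it appears. The rule should say whether any exception exists and whether planned off-week days count towards the hold. No view is given here on which rule is right.

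In the same amendment, the sponsor should bring the escalation condition in Sections 1.1, 5.1, 6 and 8.1.3 to a single wording of its own choosing, define SDRT, correct SCRT, and confirm the comparison sign in Section 6.

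The cost is amendment wording only, with no added patients, visits or data.
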